5.2.4. Recommended Dose Modifications

Every effort should be made to administer study treatment on the planned dose and schedule.

In the event of significant toxicity, dosing may be delayed and/or reduced as described below. In the event of multiple toxicities, dose modification should be based on the worst toxicity observed. Patients are to be instructed to notify investigators at the first occurrence of any adverse symptom.

Dose modifications may occur in three ways:

- Within a cycle: dosing interruption until adequate recovery and dose reduction, if required, during a given treatment cycle;
- Between cycles: next cycle administration may be delayed due to toxicity in the previous cycle;
- In the next cycle: dose reduction based on worst toxicity in the previous cycle.

5.2.5. Dose Interruptions/Delay

Patients experiencing Grade 3 or 4 potentially treatment related toxicity or intolerable Grade 2 toxicity despite supportive care should have their treatment interrupted/delayed. Appropriate follow-up assessments should be done until adequate recovery occurs as assessed by the investigator.

If a treatment interruption continues beyond Day 21 of the current cycle, then the day when treatment is restarted will be counted as Day 1 of the next cycle. A treatment delay or interruption of more than 14 days due to lack of recovery will result in discontinuation of the patient from the treatment.

A new cycle of treatment may begin only if:

- ANC $\geq 1,000/\text{mm}^3$.
- Platelets count $\geq 75,000/\text{mm}^3$.
- Non-hematologic toxicities have returned to baseline or Grade ≤ 1 severity (or, at the investigator discretion, Grade ≤ 2 if not considered a safety risk for the patient).

If these conditions are not met, treatment must be delayed by 1 week. If, after a 1-week delay, all toxicities have recovered within the limits described above treatment with PF-06650808 can be resumed. If the patient has not recovered after 1 week of delay, treatment may be delayed by 1 more week. However, initiation of the next cycle can only be delayed by a maximum of 2 weeks. Therefore, if persisting toxicity does not allow PF-06650808 treatment resumption within 35 days of Day 1 of previous cycle, treatment with PF-06650808 will be permanently discontinued.

5.2.6. Dose Reductions

Dose reductions or delays in the administration of PF-06650808 are permitted as described below for PF-06650808 related toxicity. The sponsor should be notified when dose reductions are planned and consulted for any dose reduction related questions.

Once a dose has been reduced for a given patient, all subsequent cycles should be administered at that dose level, unless further dose reduction is required. The reduced dose will be considered the maximum dose for all subsequent cycles for that patient. Doses should be reduced to the next lowest cohort dose level. Dose re-escalation is not allowed.

Patients enrolled in the first cohort should be discontinued from the study if more than 1 dose reduction is required. Patients enrolled in subsequent cohorts should be discontinued from the study if more than 2 dose reductions are required. For patients experiencing an adverse

event related to PF-06650808 that fails to recover to CTCAE Grade 1 (or within 1 grade of starting values for pre-existing laboratory abnormalities) leading to treatment delay of >2 weeks should be discontinued unless discussed with the sponsor.

The following table summarizes the actions following the toxicities observed during the study period.

Event	Action
Grade 3 or 4 nonhematologic toxicity considered at least possibly related to PF-06650808 per investigator judgment (including persistent nausea, vomiting, diarrhea despite optimal medical therapy)	
 Hold PF-06650808 infusion until recovery to Grade 0-1 or baseline and reduce by 1 dose level. Discontinue PF-06650808 if dose delay is more than 2 weeks. If toxicity reoccurs despite reduction, patient may be dose reduced again by another dose level upon recovery to grade 0-1 or baseline unless the patient is in the first dose group, then only 1 dose reduction is allowed. Prompt palliative measures are strongly encouraged (eg, anti-emetics). Patients who experience Grade 4 non hematologic toxicities despite intervention should be discontinued from the study.
Hematologic toxicity considered at least possibly related to PF-06650808 per investigator judgment 
 Grade 4 neutropenia, ie, ANC <500/mm³ (1.0 x 10⁹/L) for more than 7 days. 
 or Febrile neutropenia, ie, fever with a single temp >38.3°C or sustained temp ≥38°C for more than 1 hour with ANC <1000/mm³. 
 or Grade 4 Thrombocytopenia, ie, PLTS <25,000 mm³ (25.0 x 10⁹/L). 
 or Any grade Thrombocytopenia with bleeding. 	
 Hold PF-06650808 until recovery of ANC to ≥1.0 x 10⁹/L (1,000 cells/mm³) and platelets ≥75 x 10⁹/L (75,000 platelets/mm³). Reduce PF-06650808 by 1 dose level. If toxicity reoccurs despite dose reduction, patient may either be held until recovery and continuation at same dose, or undergo further dose reduction by another dose level unless the patient is in the first dose group, then only 1 dose reduction is allowed.
Other grade 4 hematologic toxicity considered at least possibly related to PF-06650808 per investigator judgment	
 Hold PF-06650808 until recovery to Grade 0-1 or baseline and reduce PF-06650808 dose by 1 dose level. If toxicity reoccurs despite dose reduction, patient may either be held until recovery and continuation at same dose, or undergo further dose reduction by another dose level unless the patient is in the first dose group, then only 1 dose reduction is allowed.
No recovery of toxicities within 2 weeks of scheduled PF-06650808 infusion	
 Discontinue treatment

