3.2. Dose Escalation Phase (Part 1)

A modified continual reassessment method (mCRM) targeting a DLT rate of 25% will be utilized for Part 1 (dose escalation phase) (Goodman et al, 1995; O'Quigley et al, 1990).^{7,14} Patients will be enrolled in cohorts of 2 to 4, starting with 0.2 mg/kg for the first cohort. The possible doses explored will be from a fine grid of doses ranging from 0.2 mg/kg to 6.4 mg/kg. If a high DLT rate is observed at the starting dose of 0.2 mg/kg, a lower dose such as 0.14 mg/kg (a 30% reduction from starting dose) or lower will be considered. The study may be stopped if the drug is deemed not tolerable at the lowest reduced dose. The mCRM model will determine the next dose level based on the DLT rate using a 30%, 69% and 100% dose increment for 0, 1 or 2 dose skips respectively.

Starting with the second cohort, patients will be assigned to a dose that is closest to the current MTD prediction based on a model that mCRM utilized to learn about overall dose-toxicity relationship. This model is updated after DLT assessment of each cohort. At any given point in this phase, doses can be escalated, deescalated, unchanged or revisited, but always aiming towards the target MTD. To prevent overly aggressive dose-escalation, the maximum allowed dose increase will be limited to 2 increments at a time (ie, no more than 100% dose increase at a time). In addition, if two clinically significant Grade 2 toxicities of the same type are seen in a cohort, dose escalation will be limited to no greater than 69% for the next cohort. If there is one additional case of the same Grade 2 toxicity or two other cases of clinically significant Grade 2 toxicities of the same type, dose escalation will again be limited to no greater than 69% for the next cohort; otherwise dose escalation following the mCRM algorithm will resume. Grade 2 toxicities will not be considered clinically significant if a corresponding Grade 3 toxicity exists (by NCI CTCAE v 4.03); Grade 2 toxicities without a corresponding Grade 3 toxicity will be considered clinically significant (eg, Grade 2 alopecia, dry skin, libido decrease). In addition, Grade 2 nausea, vomiting, and diarrhea will not be considered clinically significant unless it has been optimally medically managed.

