3.3. DLT Definition

Severity of AEs will be graded according to CTCAE version 4.03. For the purpose of dose escalation, any of the following adverse events which are not considered related to disease progression occurring in the first cycle of treatment (21 days) will be classified as DLTs:

Hematologic:

- Grade 4 neutropenia lasting >7 days.
- Febrile neutropenia (defined as neutropenia \geq Grade 3 and a single body temperature $>38.3^{\circ}\text{C}$ or a sustained temperature of $\geq38^{\circ}\text{C}$ for more than one hour).
- Grade ≥ 3 neutropenia with infection.
- Any grade thrombocytopenia associated with clinically significant or life-threatening bleeding.
- Grade 4 thrombocytopenia ≥ 72 hours or platelets $\leq 10,000/\text{mm}^3$ regardless of duration.

Non-hematologic:

- Grade ≥ 3 toxicities, except those that have not been maximally treated (eg, nausea, vomiting, diarrhea).
- Delay by more than 2 weeks in receiving the next scheduled cycle due to persisting toxicities not attributable to disease progression.

In addition, clinically important or persistent toxicities that are not included in the above criteria may be considered a DLT following review by the sponsor and the investigators.

Grade ≥ 3 cytokine release syndrome, infusion reaction, allergic reaction or anaphylaxis will not be considered as DLTs but may be a reason for study discontinuation and should be reviewed with the sponsor.

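### The dose-reduction table misconverts the Grade 4 neutropenia trigger: 500/mm³ is 0.5 x 10⁹/L, not 1.0 x 10⁹/L

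*Protocol*

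**What the plan says.** The action table in Protocol 5.2.6 (Dose Reductions) has a row for hematologic toxicity at least possibly related to the study drug. Its first trigger reads "Grade 4 neutropenia, ie, ANC <500/mm³ (1.0 x 10⁹/L) for more than 7 days". Its second, febrile neutropenia, requires fever "for more than 1 hour with ANC <1000/mm³". The action for the row is to hold treatment and then reduce by one level; the hold instruction begins "Hold PF-06650808 until recovery of ANC to ≥1.0 x 10⁹/L (1,000 cells/mm³", with the bracket closing after that count and a platelet condition following.

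The text above the table says how a reduction works: "Doses should be reduced to the next lowest cohort dose level", and "Dose re-escalation is not allowed". A patient in the first cohort who needs more than one reduction comes off study. In later cohorts the limit is two.

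Two neighbouring rules use neutrophil criteria separately. Protocol 5.2.5 lets a new cycle start only at an ANC of at least 1,000/mm³, among other conditions, and continues: "If these conditions are not met, treatment must be delayed by 1 week". Protocol 3.3 lists "Grade 4 neutropenia lasting >7 days" as a DLT and gives no count. SAP 7.2.1 repeats that criterion.

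**The concern.** The trigger gives two different thresholds for one event. An investigator reading in cells/mm³ would act below 500, and one reading in 10⁹/L would act below 1.0, which is 1,000/mm³. Hematology is analysed at local laboratories (Protocol 7.1.3), and the protocol supplies SI values beside several of its counts, so a site may well compare its report with the bracketed figure.

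The two readings differ for a related ANC of 0.5 to <1.0 x 10⁹/L that lasts more than 7 days. Under the bracket the patient is reduced by one level; under the 500/mm³ figure this trigger is not met. The extra reduction is permanent and uses up one of the one or two allowed. It also enters the dose-reduction and cumulative-dose summaries in SAP 9.2.4 (Treatment Administration/Compliance). Two sites could handle the same patient differently and both point to the protocol.

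**Working it through.** **Conversion.** 1 L = 10⁶ mm³, so the value in 10⁹/L = (count per mm³) x 10⁶ / 10⁹ = count / 1,000.

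**The printed figure does not reproduce.** 500 / 1,000 = 0.5, against the printed 1.0. In reverse, 1.0 x 10⁹/L = 1,000/mm³. The ratio is 1.0 / 0.5 = 2.

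**The same formula on the other counts given in both units:**

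| Count | Source | Computed (10⁹/L) | Printed (10⁹/L) | Agrees |
|---|---|---|---|---|
| ANC 1,500/mm³ | Protocol 4.1 | 1.5 | 1.5 | yes |
| Platelets 100,000/mm³ | Protocol 4.1 | 100 | 100 | yes |
| Platelets 25,000/mm³ | Protocol 5.2.6 | 25 | 25.0 | yes |
| ANC 1,000/mm³ | Protocol 5.2.6 | 1.0 | 1.0 | yes |
| Platelets 75,000/mm³ | Protocol 5.2.6 | 75 | 75 | yes |
| **ANC 500/mm³** | **Protocol 5.2.6** | **0.5** | **1.0** | **no** |

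Only one pair of six fails, and the values around it in the same row are intact.

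**Which half is intended.** The entry is labelled Grade 4 and leads with 500/mm³. The next trigger in the row applies the 1,000/mm³ limit to febrile neutropenia, and Protocol 3.3 defines that event by neutropenia of Grade 3 or worse. So 1,000/mm³ marks the Grade 3 boundary and cannot also be the Grade 4 limit. The bracket is the wrong half.

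**Size of one unneeded reduction.** Protocol 3.2 plans escalation "using a 30%, 69% and 100% dose increment for 0, 1 or 2 dose skips respectively". If the next lowest cohort lies exactly one such increment below:

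- 30% step: 1 - 1/1.30 = 23.1% of the dose removed
- 69% step: 1 - 1/1.69 = 40.8%
- 100% step: 1 - 1/2.00 = 50.0%

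For the first cohort no lower cohort exists at the outset. If the step-down dose of 0.14 mg/kg were used, the loss would be 1 - 0.14/0.20 = 30.0%. That use is an assumption: Protocol 3.2 and 9.2.1 offer 0.14 mg/kg as a cohort dose after a high DLT rate at 0.2 mg/kg, and 5.2.6 does not name it as the reduction step for an individual patient.

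**Where the effect stops.** The 1,000/mm³ rule in 5.2.5 governs the start of a new cycle under either reading. The delay-based DLT in 3.3 follows from that rule, so it does not change. The neutropenia DLT is stated by grade alone.

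**The case against.** The other side accepts the arithmetic and argues that this is a minor slip.

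- **The meaning can be recovered.** The grade label and the leading count show what was meant, and CTCAE v4.03 is in the Study Manual (Appendix 4). This stands. It limits the harm, but it does not make a wrong number in a dosing table acceptable.
- **The sponsor would hear of it.** Protocol 5.2.6 asks that the sponsor be notified when a reduction is planned. This stands as a backstop that may catch some cases. Notification is not approval, so the risk is reduced but not removed.
- **Few patients would be affected.** The patient must have a related ANC between the two limits for more than 7 days and meet no other trigger in the row. After the first days of Cycle 1, scheduled hematology is weekly through Cycle 6 and on Day 1 only from Cycle 7, so that duration usually needs consecutive low weekly counts or extra tests. Protocol 5.2.5 already calls for interruption or delay at Grade 3 or 4 related toxicity, so the hold is largely common to both readings and the reduction is what differs. All of this stands.
- **The percentages are illustrative.** Doses may be revisited or de-escalated, and the cohort steering committee may override an increment, so actual gaps between cohorts may differ. This also stands. The figures show what one misapplied reduction could cost; they are not an expected effect on the trial.

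None of these points supports the printed bracket, and no other part of the protocol corrects it.

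**Conclusion.** The concern holds. The bracketed value is twice the correct one, and the row contradicts itself. The practical risk is an unneeded and irreversible one-level reduction in a narrow group of patients, costing about 23% to 50% of the dose on the stated assumption about cohort spacing. The error runs towards caution and the intended value can be worked out from the text. It reaches the exposure and dose-reduction summaries but does not directly affect DLT counts, the mCRM or the MTD estimate. The number of patients affected cannot be estimated from the documents. Because this is an operative dosing threshold and the correct value is certain, it should be corrected.

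**What to change.** In the action table of Protocol 5.2.6, change the bracket after ANC <500/mm³ from 1.0 x 10⁹/L to 0.5 x 10⁹/L and leave the rest of the entry as it is. Protocol 3.3 and 5.2.5 need no change. The cost is a one-line protocol correction with no effect on design, sample size or analysis.

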4.1. Inclusion Criteria

Patient eligibility should be reviewed and documented by an appropriately qualified member of the investigator's study team before patients are included in the study.

Patients must meet all of the following inclusion criteria to be eligible for enrollment into the study:

1. For the dose escalation phase: Histological or cytological diagnosis of advanced/metastatic solid tumor that is resistant to standard therapy or for which no standard therapy is available.
2. For the dose expansion phase: Previously treated metastatic triple negative breast cancer that expresses Notch3 with at least one measurable lesion.
3. For the dose expansion phase: Archival core needle biopsy or prospectively collected core needle biopsy available for exploratory biomarker and Notch3 expression analysis.
4. Age ≥ 18 years.
5. ECOG Performance Status (PS) of 0 or 1.
6. Life expectancy ≥ 12 weeks.
7. Adequate Bone Marrow Function as defined by:

Absolute Neutrophil Count (ANC) $\geq 1,500/\text{mm}^3$ or $\geq 1.5 \times 10^9/\text{L}$;

Platelets $\geq 100,000/\text{mm}^3$ or $\geq 100 \times 10^9/\text{L}$;

Hemoglobin ≥ 9 g/dL.

8. Adequate Renal Function as defined by:
 - a. Serum creatinine $\leq 1.5 \times$ upper limit of normal (ULN); or
 - b. Estimated creatinine clearance ≥ 60 ml/min as calculated using the method standard for the institution.
9. Adequate Liver Function as defined by:

- a. Total serum bilirubin $\leq 1.5 \times$ ULN unless the patient has documented Gilbert syndrome;
- b. Aspartate and Alanine Aminotransferase (AST & ALT) $\leq 2.5 \times$ ULN; $\leq 5.0 \times$ ULN if there is liver involvement secondary to tumor;
- c. Alkaline phosphatase $\leq 2.5 \times$ ULN; ($\leq 5 \times$ ULN in case of bone metastasis).

10. Recovery from all prior surgical or adjuvant treatment-related toxicities, to Baseline status, or a CTCAE Grade of 0 or 1, except for toxicities not considered a safety risk, such as alopecia. Post-surgical pain will not be considered a basis for exclusion.
11. Negative serum/urine pregnancy test (for females of childbearing potential).
12. Male and female patients of childbearing potential must agree to use a highly effective method of contraception throughout the study and for at least 28 days after the last dose of assigned treatment. A patient is of childbearing potential if, in the opinion of the investigator, he/she is biologically capable of having children and is sexually active.

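### Protocol 5.2.6 prints the Grade 4 neutropenia reduction trigger as two thresholds that differ two-fold: ANC <500/mm³ and 1.0 x 10⁹/L

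*Protocol*

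**What the plan says.** The table at the end of Protocol 5.2.6 lists toxicities and the action for each. In its first hematologic row, the first event is "Grade 4 neutropenia, ie, ANC <500/mm³ (1.0 x 10⁹/L) for more than 7 days". The action is to hold the drug and then lower the dose by one level. The restart condition in that row begins "Hold PF-06650808 until recovery of ANC to ≥1.0 x 10⁹/L (1,000 cells/mm³", and the row's platelet trigger is "Grade 4 Thrombocytopenia, ie, PLTS <25,000 mm³ (25.0 x 10⁹/L".

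The text of 5.2.6 says what a reduction means. The patient moves to the dose of the next cohort down, that dose becomes the patient's ceiling, and it is not raised again. A first-cohort patient may have one reduction and later patients two. The sponsor is to be notified of planned reductions.

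Three other places bear on the point:
- Inclusion criterion 7 in Protocol 4.1 ("Adequate Bone Marrow Function as defined by") gives ANC and platelet limits in both units.
- Protocol 3.3 defines the corresponding DLT as "Grade 4 neutropenia lasting >7 days", by grade and duration, with no count printed.
- Protocol 5.2.5 sets ANC ≥1,000/mm³ as the minimum for starting any new cycle.

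**The concern.** A dosing table should give one threshold, and this line gives two. Hematology is analysed at local laboratories (Protocol 7.1.3), so a site may be reading results in either unit. A site that reads in 10⁹/L and takes the bracketed figure at face value would reduce the dose at ANC below 1,000/mm³ instead of below 500/mm³.

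By the protocol's own text, 1,000/mm³ is the Grade 3 boundary: 3.3 defines febrile neutropenia by neutropenia of Grade 3 or worse, and the 5.2.6 table writes the same event as ANC <1000/mm³. The bracketed figure therefore extends the row to prolonged afebrile Grade 3 neutropenia, for which no row of the table calls for a reduction.

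What is at stake is the reduction. The hold adds little, because 5.2.5 already bars a new cycle below 1,000/mm³. The reduction cannot be undone, and it uses one of the one or two that a patient is allowed.

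**Working it through.** **Unit check.** One mm³ is 10⁻⁶ L, so a count per mm³ times 10⁶ is a count per litre. Dividing by 10⁹ gives units of 10⁹/L, which means (count per mm³) / 1,000. Applied to every threshold that the protocol prints in both units:

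| Threshold | Source | Per mm³ | Converted (10⁹/L) | Printed (10⁹/L) | Agree |
|---|---|---|---|---|---|
| Entry ANC | 4.1, criterion 7 | 1,500 | 1.5 | 1.5 | yes |
| Entry platelets | 4.1, criterion 7 | 100,000 | 100 | 100 | yes |
| Grade 4 thrombocytopenia | 5.2.6 table | 25,000 | 25.0 | 25.0 | yes |
| Restart ANC | 5.2.6 table | 1,000 | 1.0 | 1.0 | yes |
| Restart platelets | 5.2.6 table | 75,000 | 75 | 75 | yes |
| Grade 4 neutropenia | 5.2.6 table | 500 | 0.5 | 1.0 | **no** |

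The printed 1.0 x 10⁹/L cannot be reproduced from 500/mm³. It corresponds to 1,000/mm³, and 1,000 / 500 = 2, so the two thresholds differ two-fold. The band wrongly drawn in is ANC 500-999/mm³ for more than 7 days.

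**Size of one wrongly triggered reduction.** Protocol 3.2 allows increments of 30%, 69% and 100% for 0, 1 or 2 dose skips. If the next lower cohort dose lies one such increment below the patient's dose, the fraction of dose lost is 1 - 1/(1 + increment):
- 30% increment: 1 - 1/1.30 = 23.1%
- 69% increment: 1 - 1/1.69 = 40.8%
- 100% increment: 1 - 1/2.00 = 50.0%

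The loss applies to every later cycle for that patient. The 50% figure needs a full two-skip gap. Section 3.2 expects small steps between adjacent doses once DLTs are being seen, so the lower end is more likely near the maximum tolerated dose (MTD).

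No figure is given for a first-cohort patient. The 0.14 mg/kg dose in 3.2 and 9.2.1 is a step-down for the cohort, and neither section sets it as an individual reduction level.

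**The case against.** The strongest reply is that this is a copy-editing slip that few sites would act on. The line names Grade 4 and <500/mm³ first, the two agree, and toxicity is graded by CTCAE v4.03 throughout. To misapply the row, a site would have to set aside both the grade and the leading unit. The sponsor hears of planned reductions, only about 3-4 sites take part, and 9.7 provides for regular discussion of adverse events and laboratory changes. The error also leads to a lower dose, not a higher one. All of this stands and limits the likely effect. It does not make the bracketed figure right.

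A reader might also infer a second fault, in the row for other Grade 4 hematologic toxicity, where the action is "Hold PF-06650808 until recovery to Grade 0-1 or baseline and reduce PF-06650808 dose by 1 dose level". Read literally, afebrile Grade 4 neutropenia of 7 days or less falls there and faces a stricter restart bar than prolonged or febrile neutropenia, with delay and then discontinuation to follow. The documents do not support this as a finding, for two reasons:
- The row may be meant for other cell lines; the text does not say.
- The stopping rule in 5.2.5, which applies "if persisting toxicity does not allow PF-06650808 treatment resumption within 35 days of Day 1 of previous cycle", follows from that section's own limits. A patient with ANC ≥1,000/mm³ already meets the neutrophil limit there. The last table row, "No recovery of toxicities within 2 weeks of scheduled PF-06650808 infusion", would stop such a patient only if the stricter bar governs, which is the same open question.

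At most this is a query to the sponsor about what the row covers.

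**Conclusion.** The bracketed figure is wrong as printed. The trigger should read 0.5 x 10⁹/L, and the printed value is twice that. A patient reduced because of it would lose about 23% to 50% of dose for all later cycles. This assumes that the next lower cohort dose is one permitted increment away. The documents give no basis for saying how often this would happen, and the safeguards in the protocol suggest rarely.

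Two larger consequences might be inferred, and neither is supported:
- **Dose escalation.** The neutropenia DLT in 3.3 is stated by grade and duration, so the misprint does not alter which neutropenia events count as DLTs for the continual reassessment model.
- **Choice of the recommended Phase 2 dose.** SAP 9.2.4 tabulates reductions by dose level, and Protocol 3.4 considers whether the MTD is feasible for long-term use. But 3.4 is a qualitative judgement with no rule based on reduction counts, so an effect on the chosen dose would be speculation.

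The correction is still worth making, because the line governs the dose of a cytotoxic drug and the right value is not in doubt.

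**What to change.** In the first hematologic row of the Protocol 5.2.6 table, on the Grade 4 neutropenia line, change (1.0 x 10⁹/L) to (0.5 x 10⁹/L). This is one figure in one line. It needs no extra patients, visits or tests, and no change to the DLT definition or the SAP. It can go into the next protocol amendment.

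Separately, ask the sponsor whether the row for other Grade 4 hematologic toxicity is meant to include afebrile Grade 4 neutropenia of 7 days or less. Do not add wording to that row before the answer is known. The row requires a one-level reduction, so naming brief neutropenia there could impose an irreversible reduction that was never intended.
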